## PHARMACOKINETIC AND IMMUNOGENICITY EVALUATIONS

Samples to assess both the serum concentration (pharmacokinetics) of daratumumab and the generation of antibodies to daratumumab (immunogenicity) will be obtained from all subjects according to [Table 1](#). At specified timepoints, venous blood samples (5 mL per sample) will be collected to determine serum

concentration of daratumumab and the serum will be divided into 3 aliquots (1 aliquot for pharmacokinetic analysis, 1 aliquot for antibodies to daratumumab analysis [when appropriate], and 1 aliquot as a backup).

As of Amendment 5, these samples will not be collected.

## BIOMARKER EVALUATIONS

Biomarker assessments will focus on 4 main objectives including evaluating the ability of daratumumab to reduce MRD in SMM subjects who achieve a complete response, to determine the clinical benefit (ORR, PFS, and OS) of daratumumab in subjects with genetic modifications, to evaluate the immunophenotype of SMM patients for potential immune cell contributions to daratumumab response, and to evaluate the contribution of CMMCs to progression of disease. All biomarker assessments will be performed centrally.

Bone marrow aspirates will be collected at screening and following treatment. In addition, blood samples will be obtained for assessment of CMMCs, immunophenotyping and plasma and PBMC biomarker assessments.

As of Amendment 5, these samples will not be collected.

## SAFETY EVALUATIONS

Safety will be measured by adverse events, laboratory test results, ECGs, vital sign measurements, physical examination findings, and assessment of ECOG performance status score. A QT substudy will be conducted in 30 subjects at selected sites.

## STATISTICAL METHODS

Two hypotheses will be tested:

1.  $H_0$ : CR rate  $\leq 15\%$   
 $H_a$ : CR rate  $\geq 35\%$
2.  $H_0$ : PD/death rate  $\geq 0.346/\text{patient-year}$  (median PFS  $< 24$  months)  
 $H_a$ : PD/death rate  $\leq 0.185/\text{patient-year}$  (median PFS  $> 45$  months)

This study will enroll 120 subjects (40/arm) in total. With 40 subjects per arm, each arm will have:

- 90% power to show that the true CR rate is 35% at a one-sided level of 0.05
- 80% power to show that the true PD/death rate is 0.185/patient year at a one-sided level of 0.1

If two or more treatment schedules are deemed to be effective, with 40 subjects per arm this study would have:

- 85% probability of identifying the arm with the higher CR
- 80% probability of identifying the arm with the lower PD/death rate

For the QTc substudy, assuming that the intrasubject standard deviation for change from baseline in QTc ( $\Delta\text{QTc}$ ) is 20 milliseconds and that the true difference in means is 5 milliseconds, a sample size of 25 evaluable subjects (completers) will have 80% power to show that the upper limit of the two-sided 90% confidence interval (1 sided upper 95% confidence interval) for the difference in mean QTc ( $\Delta\text{QTc}$ ) at each timepoint and baseline will be less than 20 milliseconds. To ensure 25 subjects are evaluable, the QTc substudy will enroll approximately 30 subjects.

The first primary efficacy analysis of CR rate will occur 6 months after the last subject has been randomized and will be considered as an interim analysis. The purpose of this analysis is to select an appropriate dose and schedule and enable the sponsor's decision to proceed to Phase 3.

The second primary efficacy analysis of PD/death rate will occur 12 months after the last subject has been randomized. The purpose of this analysis is to make a decision to either proceed to Phase 3 if at the interim analysis there was not enough evidence to do so or to confirm the decision made after the interim analysis to proceed to Phase 3.

Descriptive statistics will be used to summarize data. For continuous parameters, number of observations, mean, standard deviation, median, and range will be used. For discrete parameters, frequency will be summarized. For time to event parameters, Kaplan Meier estimates will be produced. When sample sizes are small, sample listings may be provided instead.

**Table 1: Time and Events Schedule Overview**

As of Amendment 5, refer to [Attachment 4](#) for a description of dose administration and study procedures for subjects who continue in the Treatment Extension Phase or who have discontinued treatment but remain in Follow-up.

|   |  | Screening Phase                     | Treatment Phase (including treatment extension/re-initiation phase)                      | EOT                            | Follow-up |
|---|--|-------------------------------------|--|--------------------------------|-----------|
|   | Notes  | within 28 days before randomization | 8-week cycles  | at 28 ± 7 days after last dose |           |
| Study treatment should be initiated within 5 days after randomization. The start of each cycle may occur ±5 days of the scheduled day in order to accommodate the schedule of the site or subject. After EOT, subjects in all treatment arms prior to PD will continue to return for disease evaluations. After PD is documented, subjects will be followed for survival; subsequent anticancer therapy, and occurrence of other malignancy. Follow-up visits, unless otherwise specified, are at Week 5, Week 9, and then q8wks during the first year after subject's first dose, then q16wks until PD and q6mos after PD. |  |                                     |  |                                |           |
| Procedures   |  |                                     |  |                                |           |
| Informed consent  | ICF must be signed before any study-related procedures are performed.  | X                                   |  |                                |           |
| Eligibility criteria  |  | X                                   |  |                                |           |
| Demography/
Medical History  |  | X                                   |  |                                |           |
| Chest X-ray   | Acceptable for screening if performed as part of SOC within 42 days before randomization   | X                                   |  |                                |           |
| FEV1 test   | Subjects with COPD   | X                                   |  |                                |           |
| ECOG  | Once a subject discontinues or completes therapy prior to PD, ECOG will only be assessed at the End-of-Treatment Visit and additionally when PD is suspected.                      | X                                   | Week 5, Week 9, and then q8wk in first year, thereafter q16wk during the Treatment Phase | X                              |           |
| 12-lead ECG   | Subjects not participating in QTc substudy. Acceptable for screening if performed within 42 days before randomization. See Table 2 for subjects in QTc substudy.   | X                                   | Pre-dose C1Wk8   | X                              |           |
| Physical exam   | including neurological, height at screening only, clinically significant abnormalities should be reported as AEs   | X                                   | symptom and disease directed exam as clinically indicated                                |                                |           |
| Vital signs, weight   | Please see Table 3 for details.  | X                                   | Please see Table 3   | X                              |           |
| Blood type and IAT results  | Includes ABO, Rh, and IAT results. A wallet card with the subject's blood type will be provided.   |                                     | C1D1 pre-dose  |                                |           |
| Laboratory Assessments   |  |                                     |  |                                |           |
| Pregnancy test  | For women of childbearing potential only within 14 days prior to randomization.  | X                                   | as clinically indicated  |                                |           |
| Hematology  |  | X                                   | Please see Table 3 for details.  |                                |           |
| HBV serology a   | Local testing for hepatitis B surface antigen (HBsAg), hepatitis B surface antibody (Anti-HBs), and hepatitis B core antibody (Anti-HBc). Refer to Section 9.5.2 . |                                     | only when re-initiating treatment  |                                |           |

|  |  | Screening Phase                     | Treatment Phase (including treatment extension/re-initiation phase)   | EOT                                | Follow-up |
|--|--|-------------------------------------|---|------------------------------------|-----------|
|  | Notes  | within 28 days before randomization | 8-week cycles   | at 28 ± 7 days after last dose     |           |
| HBV DNA test   | For subjects with serologic evidence of resolved HBV infection (ie, positive Anti-HBs or positive Anti-HBc) at Screening, HBV DNA testing by PCR must be performed locally. Refer to Section 9.5.2.  |                                     | Prior to re-initiation, Q12W during treatment, at the End of Treatment Visit, and Q12W for up to 6 months after the last dose of study treatment  |                                    |           |
| Serum chemistry  |  | X                                   | Please see Table 3 for details.   |                                    |           |
| Whole blood  | Plasma and PBMC biomarker assessments  |                                     | C1D1, C4D1  | X                                  |           |
| Whole blood  | Immunophenotyping  |                                     | C1D1, C2D1, C4D1, C8D1  | X                                  |           |
| Daratumumab PK   | During treatment phase, 1 sample to be collected before start (window -2 hrs) and 1 sample immediately after end (window +2 hrs) of dara infusion. For subjects in QTc substudy, see Table 2 for collection on C1D1 and C1Wk8. Samples to be sent to central laboratory.       |                                     | Arm A: C1D1, C1Wk8 (day of Dose #8), C2D1, C3D1, C4D1, C6D1, C8D1
Arm B: C1D1, C1Wk8, C2D1, C3D1, C4D1, C6D1
Arm C: C1D1, C1Wk8   | 4wks and 8wks after last dara dose |           |
| Daratumumab immunogenicity   | No additional sample needed for planned timepoints; will be taken from PK sample. All planned treatment phase timepoints are pre-dose only.  |                                     | Arm A: C1D1, C2D1, C4D1, C6D1
Arm B: C1D1, C2D1, C4D1, C6D1
Arm C: C1D1, C1Wk8
If an infusion reaction occurs, obtain unscheduled blood sample as soon as possible.                                    | 4wks and 8wks after last dara dose |           |
| Disease Evaluations: Subjects in Arm C will continue disease assessments per schedule below after completion of treatment in Cycle 1. For all subjects, every effort should be made to conduct disease evaluations as per schedule (window ±7 days). Refer to Section 9.2 for details |  |                                     |   |                                    |           |
| Serum disease evaluations (SPEP)   | Sample to be sent to central laboratory. IFE at screening and when CR is suspected or maintained.  | X                                   | Week 5, Week 9, and then every 8 weeks in first year, thereafter every 16 weeks until PD. b Not required on C1D1 if screening values were obtained within 14 days of C1D1                            |                                    |           |
| Urine disease evaluations (UPEP)   | Sample to be sent to central laboratory. IFE at screening and when CR is suspected or maintained. In subjects with baseline UPEP result below the level of quantification, UPEP analysis will be repeated only (1) at the time of disease progression and (2) to confirm a CR. | X                                   | Week 5, Week 9, and then every 8 weeks in first year, thereafter every 16 weeks until PD. Not required on C1D1 if screening values were obtained within 14 days of C1D1   |                                    |           |
| Serum free light chain   | Sample to be sent to central laboratory  | X                                   | Week 5, Week 9, and then every 8 weeks in first year, thereafter every 16 weeks until PD, and when CR is suspected or maintained. Not required on C1D1 if screening values were obtained within 14 days of C1D1 |                                    |           |
| β2-microglobulin   | At screening and at progression. Samples to be sent to central laboratory. At screening, within 14 days of C1D1.   | X                                   | When PD is diagnosed, or prior to any subsequent anti-MM therapy  |                                    |           |
| Calcium, albumin   | Samples to be sent to central laboratory.  | X                                   | Week 5, Week 9, and then every 8 weeks in the first year, thereafter every 16 weeks until PD. Not required on C1D1 if screening values were obtained within 14 days of C1D1                                     |                                    |           |
| Quantitative Ig  |  | X                                   | q16wk for first year, q32wk thereafter until PD   |                                    |           |

|                                      | Notes  | Screening Phase  | Treatment Phase (including treatment extension/re-initiation phase)   | EOT                            | Follow-up |
|--------------------------------------|--|--|---|--------------------------------|-----------|
|                                      |  | within 28 days before randomization  | 8-week cycles   | at 28 ± 7 days after last dose |           |
| Hemoglobin, creatinine               | At screening and during treatment, these tests are included in the local hematology and clinical chemistry tests.  |  | After completion of study treatment, obtain with disease assessments until PD.  |                                |           |
| Bone marrow aspirate/biopsy          | Acceptable for screening if performed as part of SOC within 56 days before randomization. A fresh aspirate is requested for assessment of genetic modifications, establishment of the MM clone for MRD evaluation, and immunophenotyping (all central lab). If fresh aspirate is not collected, then unstained, non-decalcified diagnostic tissue must be collected (see Section 9.2.1.7 for details). For disease confirmation, archival tissue may be used (may be local lab). | X  | At suspected CR and at 12 months and 18 months after first dose for subjects who maintain CR. Only fresh aspirate is needed for biomarker assessment. Core biopsy or aspirate is needed for clinical evaluation of CR/sCR. An additional aspirate, if feasible, will be taken within 2 months of PD diagnosis.  |                                |           |
| Blood sample for CMMCs               | As of Amendment 4, these samples will no longer be collected.  | X  | At suspected CR, and at 12 months and 18 months after first dose for subjects who maintain CR   | X                              |           |
| Skeletal radiography, or low-dose CT | Screening assessment may be performed within 56 days before randomization  | X  | Use same methodology during study as used at screening: Skeletal radiography or low-dose CT q12 months, and at biochemical progression (eg, increase in SPEP >25%) or at suspected PD. For subjects with (1) negative MRI results at baseline, (2) M-protein increase ≤25%, and (3) no other signs of clinical progression, only an MRI needs to be performed. For these subjects, low-dose whole body CT or skeletal survey does not need to be repeated unless focal lesions have been identified by MRI. |                                |           |
| MRI of spine and pelvis              | Screening assessment may be performed within 56 days before randomization  | X  | q6 months for the first 3 years, then q12 months, and at biochemical progression (eg, increase in SPEP >25%) or at suspected PD; whole body MRI per local practice or when clinically indicated.  |                                |           |
| Second primary malignancy            |  |  |   |                                | X         |
| Subsequent Anti-myeloma Therapy      | Record both treatment and response.  |  |   |                                | X         |
| Survival                             |  |  |   |                                | X         |
| Ongoing Subject Review        |  |  |   |                                |           |
| Adverse Events                       | See Section 12 for detailed instructions.  | continuous from the time of signing of ICF until 30 days after last dose of last study treatment |   |                                |           |
| Concomitant Medications              | See Section 8 for detailed instructions.   | continuous from the time of signing of ICF until 30 days after last dose of last study treatment |   |                                |           |

Abbreviations: AE=adverse event; C=cycle; CMMCs: circulating multiple myeloma cells; COPD=chronic obstructive pulmonary disease; CR=complete response; ECOG=Eastern Cooperative Oncology Group; D=day; Dara=daratumumab; ECG=electrocardiogram; EOT= End-of-Treatment; FEV= Forced Expiratory Volume (in 1 second); FFPE=formalin-fixed paraffin embedded; FLC=free light chain; IAT= indirect antiglobulin test; ICF=informed consent form; IFE=immunofixation; MRD=minimal residual disease; MRI=magnetic resonance

imaging; PBMC= peripheral blood mononuclear cell ; PK=pharmacokinetics; PD= disease progression; SAE=serious adverse event; SOC=standard of care; SPEP=serum M-protein quantitation by electrophoresis; UPEP=urine M-protein quantitation by electrophoresis; Wk=week

- a Includes HBsAg, anti-HBs, and anti-HBc. For subjects who enter extension treatment period, HBV serology (HBsAg, anti-HBs, and anti-HBc) testing is to be performed locally prior to re-initiation. HBV serology is not required at re-initiation if this was performed as part of standard of care within 3 months prior to the re-initiation or the start of extension treatment is within 3 months of last daratumumab dose.
- b If study subject already discontinued study drug and EOT took place < 6 months, treatment can be re-initiated again if there is no disease progression at the time of re-initiation of the treatment. The assessment of disease progression will be based on the last disease evaluation performed. If last disease evaluation was performed  $\geq 5$  months at treatment re-initiation, a new disease evaluation is to be performed to make sure that subject has not progressed. Every case of treatment re-initiation is to be discussed with the medical monitor prior to re-initiation.

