### HBV serology

For subjects who enter extension treatment period, HBV serology (HBsAg, anti-HBs, and anti-HBc) testing is to be performed locally prior to re-initiation. HBV serology is not required at re-initiation if this was performed as part of standard of care within 3 months prior to the re-initiation or the start of extension treatment is within 3 months of last daratumumab dose. For subjects with evidence of positive HBV serology, monitor for clinical and laboratory signs of HBV reactivation during treatment (Q12W), and for at least 6 months (Q12W) following the end of study treatment.

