### HBV DNA test

Subjects who are positive for Anti-HBc or Anti-HBs will undergo testing for hepatitis B DNA by PCR. Subjects with serologic findings suggestive of HBV vaccination (Anti-HBs positivity as the only serologic marker) and a known history of prior HBV vaccination do not need to be tested for HBV DNA by PCR. During and following study treatment, subjects who have history of HBV infection will be closely monitored for clinical and laboratory signs of reactivation of HBV as specified in the Time and Events Schedule (Table 1). Where required by local law, the results of HBV testing may be reported to the local health authorities.

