| Pregnancy test         |   | as clinically indicated  |     |           |
| HBV DNA test           | For subjects with serologic evidence of resolved HBV infection (ie, positive Anti-HBs or positive Anti-HBc) at Screening, HBV DNA testing by PCR must be performed locally. Refer to Section 9.5.2.   | Q12W during treatment, at the End of Treatment / EOT Extension Visit, and Q12W for up to 6 months after the last dose of study treatment |     |           |
| Disease Evaluations    | To be performed locally per Standard of Care. Progressive disease as determined by the Investigator must be reported to the Sponsor. Local SPEP/UPEP/FLC data are not to be recorded in the CRF. Evaluation of response is to be recorded in the CRF. | until progressive disease is determined  |     |           |

**Attachment 4: Dosing Administration and Required Study Evaluations as of Protocol Amendment 5 for Subjects Remaining in Treatment Extension or Follow Up (Continued).**

|                                      | Notes                                     | Treatment Extension Phase   | EOT | Follow-up |
|--------------------------------------|---|---|-----|-----------|
| Bone marrow aspirate                 |   | For subjects with suspected PD, bone marrow aspirate should be assessed locally per standard of care for percentage of plasma cells and reported in the CRF. After PD, no additional collections are required.  |     |           |
| Skeletal radiography, or low-dose CT |   | Use same methodology during study as used at screening and report results in the CRF:
Skeletal radiography or low-dose CT q12 months, and at biochemical progression (eg, increase in SPEP >25%) or at suspected PD.
For subjects with (1) negative MRI results at baseline, (2) M-protein increase $\leq$ 25%, and (3) no other signs of clinical progression, only an MRI needs to be performed. For these subjects, low-dose whole body CT or skeletal survey does not need to be repeated unless focal lesions have been identified by MRI. After PD, no additional assessments are required. |     |           |
| MRI of spine and pelvis              |   | q6 months for the first 3 years, then q12 months, and at biochemical progression (eg, increase in SPEP >25%) or at suspected PD; whole body MRI per local practice or when clinically indicated. Results should be entered in the CRF. After PD, no additional assessments are required.  |     |           |

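### Attachment 4 triggers HBV DNA monitoring from screening serology that no schedule requires, so an extension subject with no HBV result on file could go unmonitored

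*Protocol*

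**What the plan says.** Protocol Section 8.3 makes HBV DNA testing by PCR mandatory for subjects at risk of reactivation. The provisions meant to identify those subjects are these:

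- **Table 1, HBV DNA test row:** testing is required "For subjects with serologic evidence of resolved HBV infection (ie, positive Anti-HBs or positive Anti-HBc) at Screening". It is then done before re-initiation, every 12 weeks on treatment, at end of treatment, and every 12 weeks for up to 6 months after the last dose.
- **Attachment 4, HBV DNA test row:** the trigger is the same ("at Screening, HBV DNA testing by PCR must be performed locally"). Attachment 4 has no HBV serology row.
- **Table 1, HBV serology row:** the Screening cell is empty and the treatment-phase cell reads "only when re-initiating treatment".
- **Serology waiver (Table 1 footnote a, exclusion criterion 6.1, Section 9.5.2):** there are two alternative limbs. The first is "HBV serology is not required at re-initiation if this was performed as part of standard of care within 3 months prior" to the restart. The second is "or the start of extension treatment is within 3 months of last daratumumab dose".
- **Section 9.5.2, to which both DNA rows refer:** "Subjects who are positive for Anti-HBc or Anti-HBs will undergo testing for hepatitis B DNA by PCR", with an exception for subjects whose only marker is anti-HBs and who have a known vaccination history. In addition, "subjects who have history of HBV infection will be closely monitored".
- **Exclusion criterion 6.1:** HBsAg-positive subjects are excluded, and those with resolved infection need a PCR test. The criterion is marked as modified by Amendment 4.

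**The concern.** A monitoring rule that depends on a screening result should have a schedule that produces the result. Here neither schedule does, and Section 9.1.2 defines the screening evaluation by reference to Table 1. The second waiver limb then lets a subject move from Cycle 20 into extension untested, because it asks about the dosing gap and not about whether a result exists.

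At stake is the safety of a subject with resolved but undiagnosed HBV who stays on daratumumab outside the DNA monitoring that Section 8.3 calls mandatory. Liver tests on Day 1 of each cycle and the Section 8.3 interruption rule still protect such a subject. They act only once liver tests change or reactivation is diagnosed, however, whereas scheduled DNA testing is meant to find reactivation earlier.

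**Working it through.** The plan gives no figure to reproduce. The check is a cross-reading of the HBV provisions followed by date arithmetic.

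**1. Who is caught by which rule**

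| Subject in extension | DNA rows ('at Screening') | Section 9.5.2 |
|---|---|---|
| Positive serology found at eligibility | covered | covered |
| Positive serology found at re-initiation | not by the literal wording | covered |
| Known HBV history | only if also seropositive at Screening | covered |
| Undiagnosed resolved HBV, no result on file | not covered | not covered |

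Only the last line is a real gap.

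**2. Does the waiver reach direct continuers?** Inputs: 8-week cycles, a ±5-day window on cycle starts (Table 1), and cycles anchored to Cycle 1 Day 1 (Section 6).

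- Cycle 20 Day 1 = 19 × 56 = day 1,064; first extension slot = 20 × 56 = day 1,120.
- Nominal gap = 56 days; largest in-window gap = 56 + 5 + 5 = 66 days, below 3 months (about 91 days). An in-window continuer is therefore always waived.
- If the Cycle 20 dose is missed, the gap is 2 × 56 = 112 days (102 to 122), and the waiver fails.
- If 're-initiation' is read to mean only a restart after a stop, direct continuers fall outside the serology row altogether. Neither reading gets them tested.

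**3. Could such subjects exist?** Amendment 4, which opened the extension, is dated 28 January 2019.

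- Latest waived start = 1,064 + 91 = day 1,155, so first dose on or after 28 January 2019 − 1,155 days = 30 November 2015. With a start by the end of the Cycle 21 window (1,120 + 5 = day 1,125) the date is 30 December 2015.
- Last randomization is not stated. Amendment 5 (1 April 2020) says about 3 years of data followed the primary analysis, and that analysis came 12 months after the last randomization. This gives about April 2016. Assuming 2.5 to 3.5 years for 'about 3' gives October 2016 to October 2015.
- The exposed group therefore spans about the last 4 months of enrolment (range 0 to about 10). This is an upper estimate, because it uses the issue date. Section 17.1 forbids implementation before ethics approval, and each month of delay at a site removes a month. An assumed 3-month delay leaves about 1 month.

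**4. Is criterion 6.1 an answer?** All three last-randomization dates fall 28 to 40 months before Amendment 4, so the current wording appears to postdate enrolment. An earlier criterion 6 existed, but its text is not shown.

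**5. How much exposure remains?** For a last-enrolled subject who is in the group, has not progressed and is followed for 7 years (2,557 days):

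- From the start of extension: 2,557 − 1,120 = 1,437 days. Doses = floor(1,437/56) + 1 = 26. DNA tests = 1,437/84 = 17.1.
- From Amendment 6 (29 March 2021) to about 1 April 2023 (April 2016 plus 7 years): 733 days. Doses = 733/56 = 13.1. DNA tests = 733/84 = 8.7.

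The second pair is what a change to the current protocol could still affect.

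**The case against.** The strongest reply is that the protocol already closes the gap. Criterion 6.1 cannot be applied without serology, Table 1 requires eligibility to be checked at Screening, and the note to Section 4.2 says all criteria must be met then. On the current text, 'at Screening' therefore has something to refer to. Both DNA rows also point to Section 9.5.2, which is not tied to Screening.

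Much of this stands. Section 9.5.2 does cover every subject with a positive result or known history, so for them the trigger wording is only an editorial mismatch. A reader might infer that subjects who test positive at re-initiation escape monitoring; the documents do not support that. Criterion 6.1 helps less, because its current wording appears to postdate enrolment. Equally, a reader might infer that these subjects were never tested at entry. With the earlier criterion not shown, the documents establish neither that they were tested nor that they were not.

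A second objection is that changing the waiver now would achieve little, and this also stands. On the latest dating, the last subject's Cycle 21 slot falls by about 31 October 2019, and restarts are limited to less than 6 months after end of treatment. All entries into extension therefore appear to be past by Amendment 6.

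A third is that the affected subject is hypothetical: first dosed late enough, with no result from eligibility or routine care, with undiagnosed resolved HBV, and continued in window. That is fair. It limits the priority, but it does not supply the missing result.

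**Conclusion.** The point holds in a narrow form. Attachment 4 relies on a screening serology that neither schedule provides, and the second waiver limb let in-window Arm A/B continuers enter extension without one. The residual gap is an extension subject with undiagnosed resolved HBV and no result on file. The number of such subjects is unknown and may be zero.

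The size rests on inferred dates: last randomization about April 2016 (October 2015 to October 2016), with Amendment 4 in force from its issue date. On the central estimate, at most about 13 doses and 8 to 9 DNA tests per last-enrolled, non-progressed subject fall after Amendment 6. The 26 doses and 17 tests counted from the start of extension should not be read as what is still at stake, since about half predate the current version. No endpoint, estimand or analysis is touched. The priority is low, and the case for acting is that the remedy is cheap.

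**What to change.** In Attachment 4:

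1. Add one local HBsAg, anti-HBs and anti-HBc test for any subject still receiving daratumumab, or within 6 months of the last dose, who has no documented HBV serology. For subjects on treatment, draw it with the pre-dose hematology sample.
2. Reword the DNA-test trigger to positivity at Screening or at any later test, keeping the Section 9.5.2 vaccination exception.

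Align the Table 1 wording for consistency. The waiver text can stay, since rewriting it would have little prospective effect.

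The cost is protocol wording plus one local blood test per affected subject, possibly none. Attachment 4 assessments are already local and blood is already taken before every dose. The SAP needs no change.
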